2.1 Primary Objective

To understand the cellular and molecular response to glucocorticoids in individuals with SLE.

2.2 Secondary Objectives

1. To identify candidate targets for therapeutic interventions that could mimic the action of glucocorticoids in patients with SLE, without the significant toxicity caused by the broad range of glucocorticoid actions.
2. To test whether the transcriptional response to glucocorticoids differs between the two doses being studied.
3. To identify similarities and differences, at baseline and in response to glucocorticoids, between the transcriptome of cells from patients and those from the previously studied healthy subjects.

3 Study Design

3.1 Description of the Study Design

Potential participants will present to the NIH CC for a screening visit. Objective documentation of the diagnosis of SLE, the specific clinical manifestations, and the level of disease activity will be established. A baseline whole blood sample will be obtained at screening. Each enrolled participant will be randomly assigned to 1 of 2 methylprednisolone dose groups: 1 mg/kg or 250 mg.

All enrolled participants will return for a day-long study visit (“infusion visit”) within 75 days of the screening visit. Following collection of a pre-infusion whole blood sample, participants will receive a single IV dose of methylprednisolone (based on the dose group assignment), infused over 30 minutes. Whole blood samples will then be obtained serially, 2 and 4 hours after the start of infusion.

Participants will be discharged after collection of the 4-hour blood sample, measurement of vital signs, and documentation of any adverse events (AEs). Two follow-up phone calls will be made to document any AEs related to the methylprednisolone. If any AEs that may require treatment are documented on the follow-up phone calls, then participants will be asked to return to the NIH CC’s outpatient clinic for evaluation by the principal investigator.

We propose an adaptive study design, in which we will recruit an initial cohort of 20 participants into each of the 2 dosing groups. After processing the samples from these participants, we will perform differential expression analysis to determine if recruitment of additional participants (up to the accrual ceiling of 100) would affect the biological interpretation of the data. If additional data would be unlikely to change the study outcome, then no further recruitment will be pursued.

3.2 Study Endpoints

3.2.1 Primary Endpoint

A list of human protein-coding genes and non-coding RNAs that are differentially expressed in response to glucocorticoids in patients with SLE, for each of the studied cell types and doses.

3.2.2 Secondary Endpoints

1. A comparison of the transcriptional response to glucocorticoids between the 2 dose groups.
2. A list of protein-coding or non-coding transcripts, their corresponding proteins, and the molecular pathways representing the best candidates for targeted therapeutic alternatives to glucocorticoids.
3. Validation of the targets identified by functional studies.
4. For each cell type, a list of protein-coding or non-coding transcripts that are shared and a list of transcripts that are different, between patients with SLE and the previously studied healthy controls, at baseline or in response to glucocorticoids.

4 Study Population

4.1 Recruitment Plan

Participants will primarily be recruited from NIH study 94-AR-0066, “Studies of the Pathogenesis and Natural History of Systemic Lupus Erythematosus” (principal investigator: [name]). Because there are NIH employees enrolled in 94-AR-0066, employees may also enroll in this study.

Participants may also self-refer, be referred by outside physicians, or be referred by other investigators at the NIH CC. Any individuals who self-refer must first be enrolled onto study 94-AR-0066 to be eligible for this study.

4.2 Inclusion Criteria

Individuals must meet all of the following criteria to be eligible for study participation:

1. Aged 18-80 years.

2. Has a diagnosis of SLE based on the 1997 Update of the 1982 American College of Rheumatology Revised Criteria for Classification of SLE.
3. Currently enrolled in study 94-AR-0066.
4. Able to provide informed consent.
5. Willing to allow genetic testing.
6. Has a primary care physician or other healthcare provider who will manage all health conditions related or unrelated to the study objectives.
7. If receiving immunosuppressive therapies other than glucocorticoids for SLE, then on a stable dose (defined as no increases in dose for the 60 days prior to screening).
8.
 - A. If receiving glucocorticoid therapy and not experiencing a lupus flare at the time of the screening visit, then potential participants must be on a daily prednisone or prednisone-equivalent dose ≤ 10 mg/day and agree to undergo a glucocorticoid taper (sections 6.1 and 6.2).
 - OR
 - B. If receiving glucocorticoid therapy experiencing a lupus flare at the time of the screening visit, then potential participants must be on a daily prednisone or prednisone-equivalent dose ≤ 15 mg/day. A glucocorticoid taper will not be performed.

4.3 Exclusion Criteria

Individuals meeting any of the following criteria will be excluded from study participation:

1. Body mass index (BMI) < 18 or > 40 .
2. History of a severe allergic reaction to glucocorticoids.
3. History of a severe adverse cardiovascular or psychiatric event related to glucocorticoid administration.
4. Use of a glucocorticoid at a prednisone-equivalent dose $\square 10$ mg/day in the 15 days prior to screening (> 15 mg/day if experiencing a flare on the day of the screening visit).
5. A previously established diagnosis of an active solid or hematologic malignancy.
6. A previously established diagnosis of untreated osteoporosis. For the purpose of this study, osteoporosis is defined as a dual-energy X-ray absorptiometry (DEXA) scan obtained within 2 years of screening demonstrating a hip or spine bone mineral density T score ≤ -2.5 in men ≥ 50 years of age or in postmenopausal women.
7. A previously established diagnosis of untreated osteopenia with a high fracture risk. For the purpose of this study, osteopenia is defined as a DEXA scan obtained within 2 years of screening demonstrating a hip or spine bone mineral density T score < -1 and > -2.5 in men ≥ 50 years of age or in postmenopausal women. For the purpose of this study, a

high fracture risk is defined as a fracture risk assessment tool (FRAX) 10-year risk of major osteoporotic fracture > 20%, or a FRAX 10-year risk of hip fracture > 3%.

- 8. A previously established diagnosis of diabetes mellitus or a fasting blood glucose level \geq 125 mg/dL at the time of screening. For patients without a previously established diagnosis of diabetes mellitus and a fasting blood glucose level < 125 mg/dL at the time of screening, no additional screening tests (e.g., HbA1c or oral glucose tolerance test) will be performed. A history of glucocorticoid-induced hyperglycemia that is not present at the time of screening in the absence of treatment will not be considered an exclusion criterion.
- 9. Cancer chemotherapy within the 5 years prior to screening.
- 10. Surgery requiring general anesthesia in the 8 weeks prior to screening.
- 11. History of an infection requiring IV antibiotics in the 30 days prior to screening.
- 12. A positive test for HIV or hepatitis A, B, or C virus infection.
- 13. A positive or indeterminate test for active or latent tuberculosis (interferon gamma release assay [IGRA]) without evidence of prior treatment.
- 14. History of chronic or possible latent untreated parasitic, amebic, fungal, or mycobacterial infections.
- 15. Use of desmopressin in the 30 days prior to screening.
- 16. Use of one of the following cytochrome P450 isozyme (CYP) 3A4 inducers in the 30 days prior to screening: nafcillin, rifabutin, rifampin, St. John's wort, or troglitazone.
- 17. Use of one of the following CYP3A4 inhibitors in the 30 days prior to screening: clarithromycin, itraconazole, or ketoconazole.
- 18. Use of belimumab or rituximab within the past 180 days.
- 19. Vaccination within the past 30 days.
- 20. Pregnancy, current or in the 90 days prior to screening.
- 21. Currently breastfeeding.
- 22. Any electrocardiogram (ECG) abnormality that is clinically significant.
- 23. Any condition that, in the opinion of the investigator, contraindicates participation in this study.

Laboratory evaluations that will be used to establish eligibility are listed in sections 6 and 7, below. For exclusion criteria that involve previously established diagnoses, such as active malignancy, osteoporosis, or diabetes mellitus, any previously obtained diagnostic studies will be considered, but diagnostic testing for the sole purpose of establishing eligibility will not be performed.

Co-enrollment guidelines: Co-enrollment in other studies is permitted. Study staff should be notified of co-enrollment on any other protocol to ensure the schedules are compatible and that the volume of blood drawn for research is within NIH CC limits.

4.4 Justification for Exclusion of Special Populations

Pregnancy is an exclusion criterion because there are no adequate and well-controlled studies of glucocorticoids in pregnant people. Glucocorticoids should be used during pregnancy only if the potential benefit justifies the potential risk to the fetus. Additionally, pregnancy itself may alter the immune system, and thus may affect study results. Breastfeeding is an exclusion criterion because of the potential for serious adverse reactions in nursing infants from glucocorticoids.

People younger than 18 years are excluded from this study because there is the potential for greater than minimal risk and no prospect for direct benefit.

5 Study Agent

5.1 Disposition, Dispensation, and Accountability

The study agent, methylprednisolone sodium succinate, will be distributed and accounted for by the NIH pharmacy according to standard pharmacy procedures.

5.2 Formulation, Packaging, and Labeling

Methylprednisolone sodium succinate for injection, United States Pharmacopeia grade (USP), sold as SOLU-MEDROL sterile powder by Pfizer, Inc, is an anti-inflammatory glucocorticoid that occurs as a white, or nearly white, odorless hygroscopic, amorphous solid.³⁷ It is very soluble in water and in alcohol but is insoluble in chloroform and is very slightly soluble in acetone.

Methylprednisolone sodium succinate has the same metabolic and anti-inflammatory actions as methylprednisolone. When given parenterally and in equimolar quantities, the two compounds are equivalent in biologic activity.

The study agent is packaged in the preservative-free Act-O-Vial System, which is a single-use vial.

Each vial will be individually labeled with the patient identification number, dosing instructions, recommended storage conditions, the name and address of the manufacturer, and a statement that the agent should be kept out of reach of children.

5.3 Study Agent Storage and Stability

The study agent must be protected from light. Unreconstituted product and solution are stored at a controlled room temperature of 20°C to 25°C (68°F to 77°F). Solution must be used within 48 hours after mixing.

5.4 Randomization

Study participants will be randomized evenly to 2 dose groups. The purpose of randomization in this setting is to produce balanced dose groups where participants are comparable between groups in terms of possible confounding factors such as age, sex, or concomitant medication use. To further ensure that participants are similar in terms of SLE severity between the groups, we will adopt stratified randomization according to their disease activity using the Safety of Estrogens in Lupus Erythematosus National Assessment SLE Disease Activity Index (SELENA/SLEDAI) score on the day of enrollment. Participants will be classified into 1 of 3 disease-severity categories: low (SELENA/SLEDAI score = 0-4), intermediate (SELENA/SLEDAI score = 5-8), or high (SELENA/SLEDAI score > 9). Randomization will be carried out within each category. This stratified randomization method ensures the proportion of participants with high disease activity is the same between the dose groups.

The study statistician will design the randomization scheme. The randomization code list will be maintained by the study statistician and the study coordinator.

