A separate analysis will compare data obtained at the same time point (2 hours or 4 hours) between the high-dose and low-dose groups, to test whether there are significant differences in the transcriptional effect of glucocorticoids at the two doses. Finally, we will identify differences and similarities between the baseline transcriptome and the transcriptional response to glucocorticoids in patients with SLE recruited in this study and in healthy volunteers recruited in our previous study. Since the healthy and the SLE participants come from two different studies, they are not directly comparable in many aspects. Therefore, these results will be derived from the two studies separately and no formal comparison will be made across the two studies. We will present the baseline distribution of gene expression, the distribution of gene expression changes, and the subset of differentially expressed genes. For each cell type, we will generate a list of protein-coding or non-coding transcripts that are shared and a list of transcripts that are different between SLE patients and healthy controls.

Sequencing library preparation and sequencing batches will be carefully designed such that samples from the same participant and cell type are run in the same batch and samples from different participants are evenly distributed across batches. This will keep batch effects to a minimum in the identification of differentially expressed genes. For analyses across different participants, such as comparisons among different cell types, linear regression will be adopted with batch as a regression variable to adjust for batch difference. While prior experience suggests that library preparation is the greatest source of batch-to-batch variation in RNA-seq experiments, if the source of batch effects is unclear or cannot be adequately modeled, then the R package SVA will be used.

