15.6 Adaptive Sample Size Determination

Given the high-throughput data generation strategy of next-generation sequencing, the use of different starting materials for sequencing (mRNA, small RNA, DNA), and the use of serial sampling, standard sample size calculation methods are not appropriate in this case and an adaptive study design is a more realistic approach. Sample size consideration will be based primarily on the power to identify differentially expressed genes. The primary endpoint of the study is a list of human protein-coding genes and non-coding RNAs that are differentially expressed in response to glucocorticoids in patients with SLE, for each of the studied cell types and doses. With a sample size of 20 in each dose group, there would be 90% power to detect a change of effect size 0.72 before and after glucocorticoid by the standard paired t-test. That means, within each dose arm and for each cell type, we could detect a differentially expressed gene with 90% power if the gene expression difference before and after glucocorticoid was no less than 0.72 SD.

Due to the specific properties of RNA-seq data, an advanced mixed-effects negative binomial modeling approach will be adopted for evaluating gene expression change and the significance of the change. This will be achieved with the R package DESeq2, a widely adopted tool for differential expression analysis on sequencing data, which targets the issue of large number of genes and small number of samples. In DESeq2, data from all genes are shared and utilized in assessing the differential expression of each gene. This leads to more stable estimation of differential expression and its variability, and consequently to better power for detecting differentially expressed genes.

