Based on the data from our previous study of healthy volunteers (protocol 16-I-0126) and a bootstrap procedure, with a sample size of 20 we can detect differentially expressed genes from 0 to 2 hours after glucocorticoid infusion with a median of 0.45 log₂ fold change at a significance level of 0.05 after adjusting for multiplicity, and 0.62 log₂ fold change from 0 to 4 hours. In SLE patients, there may be higher variability in the data than what we observed in healthy volunteers. Meanwhile, the magnitude of gene expression changes is also expected to be higher, given the state of activation of many immune cells in SLE compared to healthy controls. Therefore, we estimate that the proposed initial sample size in this study will be sufficient to detect the genes associated with the effect of glucocorticoids in SLE patients.

To empirically evaluate whether this estimate is correct, we propose an adaptive study design similar to the one we performed on the study with healthy volunteers. Specifically, we will

recruit an initial cohort of 20 participants in each dose group. Based on the observed data from 20 participants, we will then assess the gain in discovery with up to 30 additional participants per group. We will perform a bootstrap procedure, sampling with replacement up to 50 units from the 20 observed participants in each group to evaluate the improvement in gene detection. For example, if the subset of genes that can be detected as differentially expressed over time and the subset of genes that can be detected as differentially expressed over the 2 doses do not change significantly above a number, then we will stop at that number. If there is change in the gene subsets, but the pathways and the biological interpretation of the data remain unchanged, then additional participants will be unlikely to change the outcome of the study and no further recruitment will be pursued. Due to the adaptive sample size determination, we will again use a nominal significance level $\alpha < 0.05$.

16 Ethics/Protection of Human Subjects

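### As printed, the randomisation strata in section 5.4 leave out a SELENA/SLEDAI score of 9 (to be confirmed), and section 15 does not use the strata in the randomised dose comparison

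*Combined protocol and SAP*

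**What the plan says.** Section 5.4 sorts everyone into three levels by the SELENA/SLEDAI score on the day of enrolment: "Participants will be classified into 1 of 3 disease-severity categories: low (SELENA/SLEDAI score = 0-4", then "intermediate (SELENA/SLEDAI score = 5-8), or high (SELENA/SLEDAI score > 9". It adds: "Randomization will be carried out within each category". The stated aim is an equal share of high-activity patients in the two dose groups.

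On the dose comparison, section 15.3 says: "A separate analysis will compare data obtained at the same time point (2 hours or 4 hours) between the high-dose and low-dose groups". The purpose is given as "to test whether there are significant differences in the transcriptional effect of glucocorticoids at the two doses". A later paragraph on sequencing batches says that for analyses across participants "linear regression will be adopted with batch as a regression variable to adjust for batch difference", with the SVA package as a fallback. Section 15.6 says that "an advanced mixed-effects negative binomial modeling approach will be adopted for evaluating gene expression change", using DESeq2. It also gives, as an example of when recruitment could stop, the case where "the subset of genes that can be detected as differentially expressed over the 2 doses do not change significantly above a number".

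Nothing in section 15 mentions SELENA/SLEDAI, disease activity or the stratum.

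**The concern.** There are two linked points.

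First, a rule that must place every participant in one of three strata has a hole at one score. Someone scoring 9 could be randomised only after an ad hoc decision, at the edge of the stratum whose balance the section sets out to secure.

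Second, stratifying makes the two dose groups more alike than simple randomisation would. An analysis that ignores the strata still counts the between-stratum variation as noise, so its standard error is too wide for the design. The contrast affected is the only randomised one. It is the first secondary endpoint, and its gene subset is one input to the sample-size bootstrap.

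Section 15.3 also does not settle whether the contrast is of expression level at 2 or 4 hours or of change from baseline. That decides which stratum term can help.

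**Working it through.** **The plan's own figure.** The only power figure is the within-arm one in 15.6: 20 participants, 0.72 SD, 90%. The normal approximation gives Φ(0.72 × √20 − 1.96) = Φ(1.26) = 89.6%, which reproduces it. The paired t-test that the text names gives 86.3% two-sided. The plan gives no power figure for the dose comparison, and nothing below depends on the 90%.

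**Coverage of the strata.** Checking each integer from 0 to 105 against 0-4, 5-8 and > 9 leaves exactly one unassigned: 9. No eligibility criterion in 4.2 or 4.3 selects by score, and the categories are defined nowhere else. The documents give no score distribution. If an assumed 1% to 10% of patients score 9, the expected number among 40 is 0.4 to 4. At 2%, the chance of at least one is 1 − 0.98^40 = 55%.

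**Same-time-point comparison.** Assumptions: 20 per arm (15.6), strata of 8, 6 and 6 per arm, a normal outcome standing in for the count model, two-sided 5%, and a true difference of 0.909 SD. That difference gives 80% power in the unstratified t-test (noncentrality 0.909 × √10 = 2.87, 38 df, critical value 2.024). R² is the share of residual variance explained by the strata. With strata balanced between arms:

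- the dose estimate is the same with or without the stratum term;
- the standard error with the term is √(1 − R²) times the one without it;
- the standard error without the term equals that of an adjusted analysis with 20 × (1 − R²) per group: 19, 18 and 17 at R² of 5%, 10% and 15%.

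Simulation with 100,000 runs per row:

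| R² (assumed) | SE ratio | Size without term | Power without | Power with | Gain (points) |
|---|---|---|---|---|---|
| 5% | 0.975 | 4.4% | 80.7% | 82.1% | 1.4 |
| 10% | 0.949 | 3.9% | 80.9% | 83.7% | 2.8 |
| 15% | 0.922 | 3.5% | 81.7% | 85.9% | 4.2 |
| 20% | 0.894 | 2.8% | 82.3% | 88.0% | 5.7 |
| 30% | 0.837 | 1.9% | 83.6% | 91.6% | 8.0 |

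With the term, size stays at 4.9% to 5.2%. Repeat simulations agree closely; they put the 15% size at 3.2% to 3.4%. At R² = 0 the term costs 2 of 38 df (critical value 2.028 instead of 2.024), and power goes from 80.0% to 79.9%.

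**Change from baseline with participant terms.** For 40 participants at two times, the design has 40 participant terms, one for time and one for dose-by-time: rank 42, residual df 80 − 42 = 38. Adding a stratum main effect leaves the rank at 42, because the participant terms already contain it, so the dose-by-time estimate and standard error do not move. Adding stratum-by-time gives rank 44 and 36 df. If the strata explain 5%, 10% or 15% of the variance of the change, power goes from 80.4% to 81.7%, 81.4% to 84.0%, or 81.9% to 86.2% (20,000 runs each).

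**The case against.** The gap at 9 could be one lost symbol. An inequality sign in exclusion criterion 4 (section 4.3) is visibly damaged in the text as read, although others there survive. The study statistician designs the scheme and could settle the boundary in practice. That is why this part is a request for confirmation, with no consequence claimed.

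On the second part, the batch sentence sits in a paragraph about library preparation, with cell-type comparisons as its example. It reaches the dose contrast only through its general wording, and the dose sentence itself names no covariate. So this is an unspecified detail, not a decision to omit the stratum. That is a fair reading, but the gap still needs filling before data are seen.

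The endpoint wording (response, effect, change) leans towards change from baseline, where a stratum main effect gains nothing. That stands, and the remedy has to cover both forms.

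The variance shares, effect size and stratum sizes are all assumed, and one normal test before FDR adjustment is not DESeq2 across many transcripts. That also stands: the figures show direction and rough scale only. Batch terms would use further degrees of freedom, and equality of the two dose estimates needs balance within strata, for which 5.4 states no blocking.

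Sparse strata could trouble the bootstrap. If 2 of 20 in an arm were in the high stratum, a resample of 20 would miss them with probability 0.9^20, about 12%. This is a practical matter for the bootstrap and does not argue against the term.

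**Conclusion.** Both parts hold. As printed, the strata omit a score of 9; whether that is intended, a slip or an extraction loss is for the sponsor to confirm, and that a 9 will occur is an assumption. Separately, the plan does not carry its randomisation strata into the only randomised contrast.

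The consequence is modest: about 1 to 4 points of power if the strata explain 5% to 15% of the relevant variance, more if they explain more, and a loss of about 0.1 point if they explain nothing. The share may be low, because activity is scored at enrolment and the infusion can follow up to 75 days after screening. There is no bias, no excess of false positives and no effect on the primary endpoint, and no claim that the recruitment decision would change. The change is worth making because it costs almost nothing and gives the dose test its correct size. Confidence is medium, since the size of the gain rests on assumed shares.

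**What to change.** - **5.4:** confirm the intended boundary against the source document and make the strata contiguous, so that every score falls in exactly one. Analyse anyone already randomised with a score of 9 in the stratum used at randomisation.
- **15.3:** state whether the dose comparison is of expression at the same time point or of change from baseline. For the former, include the three-level stratum as randomised, alongside batch. For the latter with participant terms, include stratum-by-time instead of a stratum main effect.
- **15.6:** use the same model for the dose gene subset in the bootstrap, and say how resamples with an empty stratum are handled.

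The cost is one boundary and a few sentences, plus 2 of 38 degrees of freedom before any batch terms. No patients, visits or tests are added.
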